1308 of local infection is less than 1 in 1000. This should not be a significant contributor to risks in this
1309 study as fingerticks are part of the usual care for people with diabetes.

1310 **10.1.3. Subcutaneous Catheter Risks**

1311 Participants using the study pump infusion sets will be at low risk for developing a local skin
1312 infection at the site of the infusion set placement. Though approved for 3 days of use, if a catheter
1313 is left under the skin for more than 24 hours it is possible to get an infection where it goes into
1314 the skin, with swelling, redness and pain. There may be bleeding where the catheter is put in and
1315 bleeding under the skin causing a bruise (1 in 10 risk).

CLINICAL PROTOCOL

1316 **10.1.4. Sensor Needle Risks**

1317 Participants using the continuous glucose monitor (CGM) with sensor will be at low risk for
1318 developing a local skin infection at the site of the sensor needle placement. Though approved for
1319 10 days of use, if a catheter is left under the skin for more than 24 hours it is possible to get an
1320 infection where it goes into the skin, with swelling, redness and pain. There may be bleeding
1321 where the catheter is put in and bleeding under the skin causing a bruise (1 in 10 risk).

1322 Study staff should verbally alert the participant that on rare occasions, the CGM may break and
1323 leave a small portion of the sensor under the skin that may cause redness, swelling, or pain at
1324 the insertion site. The participant should be further instructed to notify the study coordinator
1325 immediately if this occurs.

1326 **10.1.5. Risks of Hypoglycemia**

1327 As with any person having T1DM and using insulin, there is always a risk of having a low blood
1328 sugar (hypoglycemia). The frequency of hypoglycemia should be no more and possibly less than
1329 it would be as part of daily living. Symptoms of hypoglycemia can include sweating, jitteriness,
1330 and not feeling well. Just as at home, there is the possibility of fainting or seizures (convulsions)
1331 and subsequently for a few days the participant may not be as aware of symptoms of
1332 hypoglycemia. A poorly functioning CGM can periodically display falsely high glucose values,
1333 which could lead to inappropriate insulin recommendation.

1334 **10.1.6. Risks of Hyperglycemia**

1335 Hyperglycemia and ketonemia could occur if insulin delivery is attenuated or suspended for an

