1366 System for insulin dosing suggestions. The individual participant may or may not benefit from
1367 study participation.

1368 **10.3. Risk Assessment**

1369 Based on the facts that (1) adults with diabetes experience mild hypoglycemia and hyperglycemia
1370 frequently as a consequence of the disease and its management, (2) the study intervention
1371 involves feedback and advice for insulin dosing that may increase the likelihood of hypoglycemia,
1372 and hyperglycemia, (3) mitigations are in place, and have been tested in prior studies using the
1373 investigational device system in the home setting. .

1374 **10.4. General Considerations**

1375 The study is being conducted in compliance with the policies described in the study policies
1376 document, with the ethical principles that have their origin in the Declaration of Helsinki, with
1377 the protocol described herein, and with the standards of Good Clinical Practice (GCP).

CLINICAL PROTOCOL

1378 Whenever possible, data will be directly collected in electronic case report forms, which will be
1379 considered the source data.

1380 **Chapter 11 Device Cleaning Instructions**

1381 CGM cleaning instructions are provided in the Dexcom G4 PLATINUM (Professional) Cleaning and
1382 Disinfection manual (current edition). The transmitter will be cleaned with Clorox Healthcare®
1383 Bleach Germicidal Cleaner or any disinfectant product in a spray bottle containing a bleach
1384 solution of 6500 parts per million with the EPA registration number 56392-7. The transmitter will
1385 be submerged in this solution and then placed on an absorbent wipe or clean surface. Two sprays
1386 will be dispensed from the Clorox cleaner onto each side of the transmitter. A nylon brush will
1387 be used to scrub the transmitter on all sides for 30 seconds. The transmitter will be placed in the
1388 Clorox Cleaner solution for one minute. The transmitter is then rinsed under flowing tap water
1389 for ten seconds. The transmitter will then be disinfected using a disinfectant product with EPA
1390 registration number 56392-7 using similar procedures as the cleaning process.

1391 Per the pump manufacturer, the insulin pump will be cleaned with a damp lint-free cloth. Use of
1392 household or industrial cleaners, solvents, bleach, scouring pads, chemicals, or sharp instruments
1393 are prohibited. The pump should never be submerged in water. If needed, a very mild detergent,

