1620 **Chapter 13 Miscellaneous Considerations**

1621 **13.1. Prohibited Medications, Treatments, and Procedures**

1622 Participants using glulisine at the time of enrollment will be asked to contact their personal
1623 physician to change their prescribed personal insulin to lispro or aspart for the duration of the
1624 trial.

1625 The study devices (study insulin pump, study CGM) must be removed before Magnetic Resonance
1626 Imaging (MRI), Computed Tomography (CT) or diathermy treatment. Participants may continue
1627 in the trial after temporarily discontinuing use if requiring one of the treatments above.

1628 **13.2. Participant Withdrawal**

1629 Participation in the study is voluntary. Participant may withdraw at any time. For participants
1630 who do withdraw from the study, the study team will determine if their data will be used in
1631 analysis.

1632 **13.3. Confidentiality**

1633 For security and confidentiality purposes, subjects will be assigned an identifier that will be used
1634 instead of their name. Protected health information gathered for this study may be shared with
1635 the third-party collaborators. De-identified subject information may also be provided to
1636 collaborators involved in the study after the appropriate research agreement has been executed.

1637 **Chapter 14 Statistical Consideration**

1638 **14.1. Design and Randomization**

1639 This is a randomized crossover study in T1DM designed to demonstrate the efficacy of
1640 personalized feedback (PF) and decision support (DSS) over sensor-augmented pump (SAM)
1641 therapy and to establish relationships between the level of glucose variability (GV) control
1642 achievable by the intervention and individual psycho-behavioral characteristics.

1643 We plan to split the study into 4 cohorts of about 25 participants each (expected retention 20
1644 per cohort). Each cohort will continue for ~7 months and will have the structure presented in
1645 Figure 5. Following recruitment, screening, and a run-in period of SAM, participants will be
1646 randomized into one of two groups: escalation vs. de-escalation of devices and function. Each
1647 treatment modality (SAM, PF, DSS) will continue for about 8 weeks, with the last 4 weeks used
1648 to assess GV from CGM data.

1649 **Escalation: SAM → PF → DSS**

1650 **De-escalation: DSS → PF → SAM**

1651 **14.2. Sample Size**

1652 **14.2.1. Sample Size Determination:**

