1653 Sample size determination is based on our related pilot studies of DSS. We estimate that the
1654 effect size of DSS vs. SAM will be $f^2=0.22$. Power calculations (G*Power 3.1.9.2) assuming $\alpha=0.017$
1655 (corrected for multiple comparisons), 95% power, correlation of 0.55 between the repeated
1656 measures, and attrition of 20%, yield a sample size of N=100 subjects to be randomized at
1657 baseline, with N=80 subjects completing the study. PF vs. SAM assumes the same effect size. We
1658 expect that while overall DSS effect vs. PF will be smaller than vs. SAM, GV control over time will
1659 be more consistent. Aim 1.3 analysis therefore assumes a small effect size (0.15) but 5 repeated
1660 measures (bi-weekly) in each condition with higher correlation (0.65), leading to an achieved
1661 power of 97.2% for this Aim.

1662 **14.2.2. Exploration of the effect of treatment escalation vs. de-escalation:**

1663 A key advantage of the proposed study design (beyond the optimal statistical power) is the
1664 possibility to explore the glucose control and psycho-behavioral impact of features being added
1665 and/or enhanced with prescriptive components (DSS), vs. features being limited to information
1666 (PF) or even removed (SAM). We will perform this analysis by looking at the between factors in
1667 the repeated ANOVA analysis, contrasting the escalation group vs. de-escalation group. While

CLINICAL PROTOCOL

1668 not powered, this analysis will provide key insights in the future feature adaptation schemes
1669 based on the ATI.

1670 **14.3. Outcome Measures**

1671 **14.3.1. Glycemic outcomes:**

1672 The primary outcome of this study will be Glucose Variability (GV) as measured by CGM-based
1673 Coefficient of Variation (CV), as recommended by the International Consensus on Use of
1674 Continuous Glucose Monitoring. To further characterize glucose control, we will compute other
1675 CGM Consensus outcomes as well:

- 1676 • Average
- 1677 • Percent in different ranges:
 - 1678 ○ <50 mg/dL
 - 1679 ○ <54 mg/dL
 - 1680 ○ <60 mg/dL
 - 1681 ○ <70 mg/dL
 - 1682 ○ ≤70-≤180 mg/dL
 - 1683 ○ >180 mg/dL
 - 1684 ○ >250 mg/dL
 - 1685 ○ >300 mg/dL
- 1686 • SD and coefficient of variation
- 1687 • LBGI, HBGI, ADRR

1688 Each modality of treatment will be assessed using the last 4 weeks of CGM recordings, as we
1689 expect most of the GV benefits of each intervention to be realized within the first 4 weeks of the

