1690 intervention, and a minimum of 24 days of data is considered optimal for CGM-based CV
1691 determination.

1692 **14.3.2. Glucose Variability Reduction Achieved with CGM-based expert systems:**

1693 General linear models (GLM) (repeated measures ANOVA) will be used to assess the significance
1694 of the differences in average response between SAM, PF, and DSS across appropriate CGM-based
1695 metrics. The particular design of the clinical study allow for Aims 1.1, 1.2, and 1.3 to each be
1696 addressed independently in a randomized crossover analysis, as shown in Figure 4. While the
1697 randomized order of the interventions (escalation vs de-escalation) allows for an objective
1698 assessment of the average efficacy of each of them, we will introduce the order as a fixed factor
1699 to verify if significant study effects can be detected. Finally, we will study the evolution of GV
1700 within each modality period: GV and other CGM-based outcomes will be computed bi-weekly
1701 (the minimum length of time for precise GV assessment) and entered in a repeated measures

CLINICAL PROTOCOL

1702 GLM analysis; within-subject contrast (linear and polynomial) using 5 repeated measures per
1703 condition to explore the evolution of the glycemic outcomes in time; Aim 1.3.

1704 **14.4. Exploration of the effect of treatment escalation vs. de-escalation**

1705 A key advantage of the proposed study design (beyond the optimal statistical power) is the
1706 possibility to explore the glucose control and psycho-behavioral impact of features being added
1707 and/or enhanced with prescriptive components (DSS), vs. features being limited to information
1708 (PF) or even removed (SAM). We will perform this analysis by looking at the between factors in
1709 the repeated ANOVA analysis, contrasting the escalation group vs. de-escalation group. While
1710 not powered, this analysis will provide key insights in the future feature adaptation schemes
1711 based on the ATI.

1712 **14.5. Psychological and Behavioral Questionnaires**

1713 *Quantitative* data on usability and satisfaction will be analyzed using simple descriptive statistics.
1714 In addition, we will analyze scores from the measures in the psychosocial assessment battery to
1715 determine if changes occur over time and between groups. Using SPSS 26, we will construct
1716 predictive models in the general linear modeling (GLM) framework to examine each set of

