1717 psychological factors (e.g., INSPIRE survey) over time, and their association with glycemic
1718 outcomes. Group assignment and Study Phases will be the primary covariate.

1719 **14.6. Baseline Descriptive Statistics**

1720 Baseline demographic and clinical characteristics of the cohort of all randomized participants will
1721 be summarized in a table using summary statistics appropriate to the distribution of each
1722 variable. Descriptive statistics will be displayed overall and by treatment group.

1723 Will include:

- 1724 • Age
- 1725 • HbA1c collected at randomization and study end
- 1726 • Gender
- 1727 • Race/ethnicity
- 1728 • CGM use before enrollment
- 1729 • Diabetes duration
- 1730 • BMI

1731 **14.7. Device Issues**

1732 We will count each time the participant interacted with the study Personalized Feedback and
1733 Decision Support System and perform a Wilcoxon paired rank test to determine if any differences
1734 exist in system interactions.

1735 **Chapter 15 Data Collection and Monitoring**

1736 **15.1. Case Report Forms and Device Data**

1737 The study data are collected through a combination of case report forms (electronic and paper)
1738 and electronic device data files obtained from the software and individual hardware
1739 components. These electronic device files and electronic CRFs are considered the primary source
1740 documentation.

1741 When data are directly collected in electronic case report forms, this will be considered the
1742 source data. Records will be maintained in accordance with ICH E6 and institutional regulatory
1743 requirements for the protection of confidentiality of participants.

1744 **15.2. Study Records Retention**

1745 Study documents will be retained for a minimum of 2 years after study close out. These
1746 documents may be retained for a longer period, however, if required by local regulations. No
1747 records will be destroyed without the consent of the Principal Investigator. It is the responsibility
1748 of the Principal Investigator to inform all co-investigators when these documents no longer need
1749 to be retained.

1750 **Chapter 16 Ethics/Protection of Human Participants**

1751 **16.1. Ethics Standard**

1752 The investigator will ensure that this study is conducted in full conformity with Regulations for
1753 the Protection of Human Participants of Research codified in 45 CFR Part 46, 21 CFR Part 50, 21
1754 CFR Part 56, and/or the ICH E6.

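### The main comparison of hypoglycemia between modes leaves out weeks 1–4 of each mode, and no adverse-event summary by mode is planned

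*Combined protocol and SAP*

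**What the plan says.** Section 14.3.1 names CV as the primary outcome. It then lists further CGM outcomes: the average, time below 50, 54, 60 and 70 mg/dL, time in and above range, SD, LBGI, HBGI and ADRR. After the list it states: "Each modality of treatment will be assessed using the last 4 weeks of CGM recordings". No listed outcome is excepted. Section 1.3.1 has the same sentence after a shorter list that includes the four low-glucose ranges but not LBGI. Two reasons are given. The investigators "expect most of the GV benefits of each intervention to be realized within the first 4 weeks of the" intervention, and 24 days of data are regarded as the optimal minimum for CV. Sections 1.4 and 14.1 give the phase length: each "treatment modality (SAM, PF, DSS) will continue for about 8 weeks, with the last 4 weeks used" to assess GV.

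Section 14.3.2 adds a time-course analysis: "within each modality period: GV and other CGM-based outcomes will be computed bi-weekly". It uses five repeated measures per condition and is tied to Aim 1.3.

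On risk, Section 10.3 says that the intervention "involves feedback and advice for insulin dosing that may increase the likelihood of hypoglycemia". Under Sections 12.1.1 and 12.3.1, hypoglycemia short of the severe definition is not recorded as an adverse event unless it is linked to an adverse device effect. Adverse events and glucose values below 54 mg/dL are asked about at Visits 3 to 6 for the whole interval since the last visit. Accumulated events go to the DSMB (12.3.2), and a Medical Monitor reviews every severe hypoglycemia and DKA event (12.12).

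Chapter 14 describes no analysis of adverse events. Section 14.7, although headed Device Issues, deals with system use: "We will count each time the participant interacted with the study Personalized Feedback and" Decision Support System.

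**The concern.** A late window suits an efficacy question about settled control, because it lets the mode take effect before it is measured. That reasoning does not carry over to hypoglycemia, where the period just after a mode change is part of what a safety reader wants to see. Mode change and training take place at the start of each phase, so first exposure to new bolus logic and dosing advice falls in the weeks outside the window.

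Because lows short of severe are mostly not adverse events under this protocol, CGM is the main quantitative record of them. If the main CGM comparison by mode uses only the second half of each phase, and adverse events are not summarised by mode, the trial can report DSS as neutral or better on hypoglycemia without having set its first four weeks beside those of SAM. Participants who stop device use early in a mode, including those who meet the discontinuation criteria in Section 12.11.1, have no last-4-weeks value for that mode.

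**Working it through.** **Inputs from the documents.** Phase length: about 8 weeks (1.4, 14.1), with a minimum of 8 weeks (Chapters 6 and 7). Window: last 4 weeks. Modes: 3. Randomized: 100, attrition 20% (14.2.1), so completers = 100 × (1 − 0.20) = 80, the plan's figure. Bi-weekly measures: 5 per condition (14.3.2).

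**The plan's own reason for the window.** 4 weeks × 7 = 28 days, which exceeds the 24 days cited for CV. The window is adequate for CV. Neither stated reason refers to hypoglycemia or safety.

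**Share of exposure outside the window.** Share = (L − 4)/L for a phase of L weeks.
- L = 8: 4/8 = 50%. Per participant, 3 × 4 = 12 of 3 × 8 = 24 randomized weeks.
- A phase longer than the minimum raises the share. For example, L = 10 gives 6/10 = 60%.
- For 80 completers at L = 8: 80 × 3 × 4 = 960 of 80 × 3 × 8 = 1,920 participant-weeks.

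**What an early difference would look like (assumed values, not from the documents).** Suppose DSS had an excess of d percentage points in time below 70 mg/dL, confined to weeks 1–4. The last-4-weeks contrast is 0 and the whole-phase contrast is d × 4/8.
- d = 1: 0 against 0.5 points.
- d = 3: 0 against 1.5 points.

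Similarly, if time below 54 mg/dL were 1.0% in weeks 1–4 and 0.4% in weeks 5–8, the window reports 0.4% and the whole phase is (1.0 + 0.4)/2 = 0.7%. These show how the rule works and are not estimates.

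**Does the bi-weekly analysis fill the gap?** Four weeks hold at most 4/2 = 2 two-week windows, so a series of five must use data from weeks 1–4. To that extent the early weeks are analysed. Four limits remain:
- The stated aim is to explore evolution over time by trend contrasts.
- It is assigned to Aim 1.3, which compares DSS with PF, not with SAM.
- It refers to other CGM-based outcomes without naming a hypoglycemia measure.
- Eight weeks hold 8/2 = 4 non-overlapping windows, while five need 10 weeks, so its coverage is not fully defined.

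**Do parameter updates act early?** The optimization routine uses the previous 30 days of data. Escalation participants already have that history when DSS starts. De-escalation participants with a run-in of 14 to 28 days would reach 30 days between day 30 − 28 = 2 and day 30 − 14 = 16 of DSS. The timing of updates is not stated, and run-in can be extended, so this makes early action plausible and does not establish it.

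**Early stoppers.** A person who stops device use in weeks 1–4 has no data in weeks 5–8 of that mode. Section 13.2 leaves the use of withdrawn participants' data to the study team, with no rule stated.

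**The case against.** The strongest reply is that the early weeks are covered. Section 14.3.2 says that "GV and other CGM-based outcomes will be computed bi-weekly" in each modality period, and the natural reference of other outcomes is the list in 14.3.1. An outcome computed every two weeks in each mode is already a level by mode and time. This stands in part. A reader might infer that weeks 1–4 are discarded and hypoglycemia is seen only in the last 4 weeks, but the documents do not support that. What is missing is a stated by-mode hypoglycemia comparison that includes those weeks.

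Second, Sections 1.4 and 14.1 tie the last 4 weeks to GV, so the window might not be meant for every listed metric. That reading is possible. It would leave the hypoglycemia metrics with no stated window, and the same sentence of the plan would need changing.

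Third, safety is handled in Chapter 12 over whole phases. Events are collected at each mode change and at exit, participants are asked to call about lows, and the DSMB and Medical Monitor review what is reported. This stands: severe events in weeks 1–4 are not lost, including those that end device use. The DSMB Charter and Medical Monitor document are separate, and whether they contain tables by mode cannot be judged here. Neither review is described as a comparison of modes.

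Fourth, a reader might infer that risk peaks early. No section says so. The pilot's 48-hour periods in 24 people point the other way: with DSS, median time below 70 mg/dL fell from 3.2% to 0.9%, LBGI fell from 2.5 to 1.6, and there were no adverse events. Section 10.3 also cites tested mitigations. Two days of observation do not settle four weeks of home use, but they give no support for an early excess.

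Fifth, Section 10.1.5 says of low blood "sugar (hypoglycemia). The frequency of hypoglycemia should be no more and possibly less than" in daily living. It is tempting to say that the trial cannot check this statement. It is a risk disclosure against usual life, not a hypothesis, and with no usual-care arm no SAM/PF/DSS table would test it.

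**Conclusion.** The point holds as a gap in the planned comparison. As written, 14.3.1 applies a window justified only by GV benefit and CV precision to all listed CGM outcomes. The main by-mode hypoglycemia comparison therefore omits at least half of each mode's exposure (960 of 1,920 participant-weeks for 80 completers) and anyone who stops device use in weeks 1–4. The early weeks enter only an exploratory time-course analysis, and Chapter 14 has no by-mode adverse-event summary.

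This rests on reading the window sentence as covering the list it follows, and on phases of at least 8 weeks. It does not show that hypoglycemia is more frequent early, that an early excess would go unseen by the DSMB or Medical Monitor, or that the CV endpoint or sample size needs revision. It is a worthwhile, inexpensive improvement that should be made before analysis.

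**What to change.** Keep the last 4 weeks (weeks 5–8 of an 8-week phase) for CV. Make two additions:

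1. In 14.3.1, state that time below 54 and below 70 mg/dL and LBGI will also be summarised by mode (SAM, PF, DSS) over all days from mode activation to the end of that mode, with weeks 1–4 shown separately. Include everyone who started the mode, whether or not they completed it. Say that this rule, rather than the case-by-case decision in 13.2, governs these tables.
2. In Chapter 14, add a table of severe hypoglycemia, DKA or ketosis, SAEs and adverse device effects by mode in use at onset, with exposure time and events per participant-month, for the same participants.

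Both are descriptive, use CGM and adverse-event data already collected, and leave the primary endpoint and sample size unchanged. The costs are a few tables and safety figures that may look less favourable than the late-window ones. There is also a limit on interpretation: no washout between modes is described, so weeks 1–4 may carry over effects of the preceding mode. A footnote should say so, and showing the tables by sequence as well would help the reader judge it.

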CLINICAL PROTOCOL

409 **Aim 1.1** the superiority of the PF over Sensor-augmented mode (SAM) in controlling GV. PF is a
410 system designed to provide patients with *actionable information* about glucose control in general
411 and GV in particular (e.g. estimated HbA1c (eA1c), risk of hypoglycemia, and activity level);

412 **Aim 1.2** the superiority of the DSS over SAM in controlling GV. DSS is a CGM-based system that
413 includes PF and further assists with treatment recommendations for common metabolic
414 challenges;

415 **Aim 1.3** the overall non-inferiority of DSS over PF intervention to control GV and superiority of
416 DSS to maintain tight glycemic control over time (lower variations of GV in time).

417 **Aim 2 (personalization of treatment policy)** We hypothesize that the participants in this study
418 will have technology intervention preferences (e.g. PF or DSS) that can be predicted by key
419 psychosocial and behavioral parameters and are prognostic of the level of GV control achievable
420 by the intervention. We will:

421 **Aim 2.1** confirm that technology acceptance and trust are predictive of the level of GV control
422 achieved during the study (see Aim 1), regardless of the type of DSS system in use. We
423 hypothesize that technology acceptance will correlate negatively with GV: i.e. higher technology
424 acceptance leads to lower GV;

425 **Aim 2.2** explore the impact of technology expectations and experience on the performance of
426 each type of technology intervention (SAM, PF, DSS). For example, higher expectation will
427 negatively correlate with GV for the SAM treatment, but not the DSS treatment.

428 **Aim 2.3** assess the correlation between relevant psycho-behavioral traits with the performance
429 of PF vs DSS, identifying potential pathways to the corresponding optimal technology-based
430 treatment policies.

431 **1.3. Outcomes**

432 **1.3.1. Glycemic outcomes**

433 The primary outcome of this study will be Glucose Variability (GV) as measured by CGM-based
434 Coefficient of Variation (CV), as recommended by the International Consensus on Use of
435 Continuous Glucose Monitoring. To further characterize glucose control, we will compute other
436 CGM Consensus outcomes as well:

437 Average

438 Percent in different ranges:

439 ○ <50 mg/dL

440 ○ <54 mg/dL

[figure not shown]
CLINICAL PROTOCOL

- 441 ○ <60 mg/dL
- 442 ○ <70 mg/dL
- 443 ○ ≤70-≤180 mg/dL
- 444 ○ >180 mg/dL
- 445 ○ >250 mg/dL
- 446 ○ >300 mg/dL

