836 Once all training activities are completed, the participant will be given adequate supplies and
837 study devices to last until the subsequent clinic visit. An appointment for Visit 4 will be scheduled

838 **6.3. Home Use of DiAs in Phase 1 Mode**

839 The participant will complete a minimum of 8 weeks of DiAs use in Phase 1 Mode at home. During
840 the course of Phase 1, participants will complete EMA surveys and post-phase questionnaires.

841 **6.3.1. Phase 1 EMA Surveys**

842 Over the course of 2-3 days every two weeks of Phase 1, the participant will be asked to complete
843 a “Daily Diary” with 3-5 entries of 3-4 questions each day, for a minimum total of 48 entries per
844 participant during each Phase.

845 **6.3.2. Post-Phase 1 Questionnaires Week 7**

846 Participants randomized to escalation will be sent the following questionnaires on week 7 (day
847 42 of Phase 1) and will be asked to complete them within 1 week:

- 848 • Pittsburgh Sleep Quality Index

CLINICAL PROTOCOL

- 849
- Hyperglycemia Avoidance Scale

850 **6.3.3. Post-Phase 1 Questionnaires Week 8**

851 Participants randomized to escalation will sent the following questionnaires on week 8 (day 49
852 of Phase 1) and will be asked to complete them within 1 week:

- 853
- Confidence in Diabetes Self-Care Scale
- 854
- T1-Diabetes Distress Scale
- 855
- Hypoglycemia Fear Survey

856 **6.4. Visit 4 – Phase 2 Initiation**

857 All participants in each randomization scheme use PF in Phase 2. Phase 2 initiation may be
858 conducted either via web conference or an office visit. The participant will remotely receive a
859 mode change for Phase 2. Study staff will review the features of the Personalized Feedback (PF)
860 mode and answer any questions. Participant will have a blood/urine pregnancy test that must be
861 negative in order to continue to participate in this study.

862 **6.4.1. Training on Phase 2 DiAs Mode**

863 The participant will be trained on the following features of the Personalized Feedback System:

- 864
- **Tracking of estimated HbA1c:** When properly calibrated, eA1c is within 0.3% of
865 reference HbA1c on average, and within 1% of HbA1c >95% of the time.
- 866
- **Hypoglycemia Risk Indicator:** Provides an indication of the current risk for
867 hypoglycemia.
- 868
- **Insulin Sensitivity Profile & Indicator:** Tracks changes in insulin sensitivity (SI) and
869 creates daily and monthly SI profiles.
- 870

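### PF is always given in Phase 2, so PF vs SAM (Aim 1.1) and the overall DSS vs PF comparison (Aim 1.3) rest on unstated assumptions about period effects and carryover

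*Combined protocol and SAP*

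**What the plan says.** Section 14.1 gives two sequences only: escalation (SAM, PF, DSS) and "De-escalation: DSS → PF → SAM". Sections 6.4 and 7.4 both confirm the consequence: "All participants in each randomization scheme use PF in Phase 2".

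Section 1.2 sets three comparisons on glucose variability. Aim 1.1 is "the superiority of the PF over Sensor-augmented mode (SAM) in controlling GV". Aim 1.2 is DSS over SAM. Aim 1.3 begins with "the overall non-inferiority of DSS over PF intervention to control GV and superiority of" DSS in keeping control tight over time.

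Section 14.3.2, repeated in 1.3.2, plans a repeated-measures ANOVA and says the design lets each of the three aims be "addressed independently in a randomized crossover analysis, as shown in Figure 4". On order, it says that randomizing the sequence permits an objective "assessment of the average efficacy of each of them, we will introduce the order as a fixed factor". Section 14.4 adds an exploratory look at the between-participant factor in "the repeated ANOVA analysis, contrasting the escalation group vs. de-escalation group", described there as not powered. No period term and no condition on period effects or carryover appears in either section. Study phase is named as a model term only for the questionnaires, in 14.5: "Group assignment and Study Phases will be the primary covariate".

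**The concern.** A crossover protects a treatment comparison from period effects because each treatment is seen in more than one period. Here that holds for SAM and DSS, which swap between Phases 1 and 3. It does not hold for PF: PF and Phase 2 are the same cells of the design.

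Two of the three Aim 1 comparisons on the primary outcome (CGM CV) therefore depend on how CV would move over the trial with no change of mode. If CV falls for everyone after Phase 1 and then levels off, PF looks better than it is against both SAM and DSS. The opposite curvature makes it look worse. A result reported as a randomized crossover comparison would be partly a comparison of Phase 2 with the average of Phases 1 and 3.

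Carryover is a second unstated condition. In de-escalation, PF follows directly on DSS, which supplies updated treatment parameters (7.2).

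**Working it through.** **Inputs.** Sequences from 14.1. From 14.2.1: 80 completers of 100 randomized, α = 0.017, correlation 0.55, effect size 0.22 for DSS vs SAM and for PF vs SAM, and for Aim 1.3 effect size 0.15 with five measures and correlation 0.65. From the DSS pilot in 1.1.2: CV 0.36 ± 0.08 and 0.33 ± 0.06, over 48-hour periods. Not in the documents: the SD of a 4-week CV, and any estimate of period effects.

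**The plan's own figures.** Noncentrality λ = N·m·f²/(1−ρ).
- f = 0.22, m = 2: λ = 80·2·0.0484/0.45 = 17.2, power 95.4% (plan: 95%); 80/(1−0.20) = 100.
- Aim 1.3, f = 0.15, m = 5: λ = 80·5·0.0225/0.35 = 25.7, power 97.2% (plan: 97.2%).

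Both reproduce with 0.22 read as f; as f² it would need only 20 participants. The arithmetic is sound but takes the PF contrasts as estimable.

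**Expected cell means**, with period effects p1, p2, p3 (the sequence term is omitted because it cancels within sequence):

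| Sequence | Phase 1 | Phase 2 | Phase 3 |
|---|---|---|---|
| Escalation | SAM + p1 | PF + p2 | DSS + p3 |
| De-escalation | DSS + p1 | PF + p2 | SAM + p3 |

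Mean, sequence, period (two parameters) and treatment (two parameters) make six parameters, but the design matrix has rank 5. Only the sum PF + p2 is identified. DSS−SAM is estimable; PF−SAM and DSS−PF are not. Adding the SAM run-in as a period 0 does not change this.

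**Bias with the sequences weighted equally**, where c = p2 − (p1+p3)/2:
- PF−SAM: ½[(p2−p1) + (p2−p3)] = +c
- DSS−PF: ½[(p3−p2) + (p1−p2)] = −c
- DSS−SAM: ½[(p3−p1) + (p1−p3)] = 0

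| Period pattern | PF−SAM | DSS−PF | DSS−SAM |
|---|---|---|---|
| (0, −1, −2), linear | 0 | 0 | 0 |
| (0, −1, −1), plateau | −0.5 | +0.5 | 0 |

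A linear phase term leaves the second row unchanged.

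**Size (illustration).** SD = √((8²+6²)/2) = 7.07 points. SE = 7.07·√(2·0.45/80) = 0.75. Critical t (79 df) = 2.438, so the smallest significant difference is 1.83. False-positive rates for PF vs SAM, from the noncentral t with noncentrality c/SE:

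| c (points) | c/SE | False-positive rate |
|---|---|---|
| 0 | 0 | 1.7% |
| 0.5 | 0.67 | 4.3% |
| 0.75 | 1.0 | 8.0% |
| 1.5 | 2.0 | 33.6% |

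For c = 0.5 the rate is 11.0% at SD 4, 7.3% at SD 5 and 3.7% at SD 8. A plateau gives c equal to half the drop, so c = 1.5 needs a 3-point drop, as large as the whole pilot DSS effect.

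**Can the planned checks show c?** It shifts PF equally in both sequences, so it drops out of the order main effect and of every order-by-mode contrast. In simulation (6,000 trials per scenario) with plateau drops of 1, 1.5 and 3 points, PF vs SAM rejects in 4.0%, 8.2% and 33.8%. The order factor, tested at 0.05, rejects in 5.0%, 5.6% and 5.1%; the order contrast for PF against the other two modes in 5.3%, 4.9% and 4.6%.

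**Carryover, with c = 0.** A 1-point reduction carried from DSS into PF shifts PF−SAM by −0.5 and DSS−PF by +0.5 (PF vs SAM false-positive rate again 4.3%). A 1-point reduction carried from PF into SAM in de-escalation shifts PF−SAM and DSS−SAM by +0.5.

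No error rate is given for Aim 1.3. Its effect size of 0.15 belongs to a five-measure analysis (with two measures the power would be 77.7%), and the plan gives no non-inferiority margin.

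**The case against.** Each pair of modes does occur in both relative orders, so each can be analysed as a two-treatment crossover, and constant and linear period effects cancel. That is correct. But the PF vs SAM pair uses Phases 1–2 in one sequence and Phases 2–3 in the other. Period effects cancel only if the step from Phase 1 to 2 equals the step from Phase 2 to 3, which is c = 0, and the plan does not say so.

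The plan also limits the problem. The SAM run-in (14 days or 4 weeks) and the use of only the last 4 weeks of each phase reduce early learning, and the discarded weeks also act as a partial washout. The documents do not say whether DSS-updated parameters stay in force under PF, so that carryover is possible rather than shown. These points make large values of c or carryover less likely without excluding them. The bi-weekly within-phase contrasts may show drift but do not identify c.

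A plateau would often leave a trace. The DSS−SAM-by-order contrast estimates p3 − p1 and, at α = 0.05, would reject in about 26%, 51% and 98% of trials for drops of 1, 1.5 and 3 points. This stands, and it is useful, but it measures p3 − p1, not c, and 14.3.2 does not name it. A pattern such as (0, −0.75, 0) has c = −0.75 and leaves no trace: PF vs SAM rejects in 7.7% and no order or interaction test exceeds 5.1%. The PF-by-order contrast does respond to carryover into PF, but weakly: about 12% for 1 point and 63% for 3 points (SE 1.30, 78 df, α = 0.05).

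Figure 4 is not reproduced in the text available, so a condition stated inside it cannot be excluded. Its caption and the surrounding text give none, and no figure can vary the position of PF.

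**Conclusion.** The concern holds. With unrestricted period effects, PF−SAM and the overall DSS−PF difference are not estimable from these two sequences. The statement in 14.3.2 and 1.3.2 is right, as regards period effects, only for DSS vs SAM, and that comparison also needs no differential carryover. This follows from the design and needs no numerical assumption.

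The practical size is unknown. The false-positive rates above rest on a 48-hour pilot SD, correlation 0.55, 80 completers and assumed values of c. In SD-free terms, curvature of one standard error of the contrast raises a nominal 1.7% to 8.0%. No conclusion is drawn here about the part of Aim 1.3 on variation in GV over time.

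This should be fixed before analysis because it changes what can be concluded from two of the three Aim 1 comparisons.

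**What to change.** 1. In 14.3.2 and 1.3.2, replace the statement about independent crossover analyses with wording to this effect: *Assuming no differential carryover, DSS vs SAM is identified when period effects are allowed. PF−SAM and DSS−PF are reported as conditional on no period curvature (c = 0) and no differential carryover into or out of PF, with the two sequences weighted equally.*
2. Report PF−SAM and DSS−PF over a prespecified range of c in both directions, with the value of c at which each conclusion changes. The range can be tied to the data: d = p3 − p1 is half the difference between sequences in DSS−SAM. If period effects move in one direction only (to be stated as an assumption) and there is no differential carryover, |c| ≤ |d|/2; use the outer confidence limit of d. Do not present a linear phase term as protection.
3. Optionally, as support for Aim 1.2, report the Phase 1 comparison of DSS with SAM adjusted for run-in CV. It is free of carryover but does nothing for PF.

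**Cost.** SAP wording, one sensitivity table and one supportive model. Aims 1.1 and 1.3 lose the unconditional randomized claim. The bound is wide: under the illustrative assumptions the SE of d is 0.75, so even an estimate of 0 has 98.3% limits of ±1.83 and allows |c| up to 0.91, at which the PF vs SAM false-positive rate is about 12%. To be robust over that range PF−SAM would have to exceed about 1.83 + 0.91 = 2.74 points, for which power at the planned 3.11 points (2·0.22·7.07) is about 69%. The bound does not cover non-monotone patterns, so the tipping value of c should be reported regardless. The Phase 1 comparison has about 47% power (40 per arm, SE 1.32 with an assumed run-in correlation of 0.55, α = 0.017, 3.11 points).
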